#### **8.1.7 Protocol Deviations**

The major protocol deviations will be listed.

### **8.2 Safety Assessments**

#### **8.2.1 Adverse Events**

The frequency and incidence of TEAEs will be summarized by System Organ Class (SOC) and Preferred Term (PT) by treatment of study A01 and overall.

Following summaries will be presented:

- Overall summary of TEAE (Table 14.3.1.1)
- TEAEs by SOC and PT (Table 14.3.1.2)
- TEAEs by SOC, PT and time of onset (Table 14.3.1.3)
- TEAEs by SOC, PT and severity (Table 14.3.1.4)
- TEAEs leading to discontinuation of study medication by SOC and PT (Table 14.3.1.5)
- Serious TEAEs by SOC and PT (Table 14.3.1.6)
- TEAEs by SOC, PT and relationship (Table 14.3.1.7)
- [REDACTED]

- Adverse drug reactions by SOC and PT (Table 14.3.1.9)
- Serious adverse drug reactions by SOC and PT (Table 14.3.1.10)
- TEAEs by SOC and PT for AEs with frequency  $\geq 3\%$  (or 5%) (Table 14.3.1.11)
- [REDACTED]

For each of the summaries will be done at the subject level - multiple occurrences of the same event within a subject will be counted once in the summaries by SOC and PT; multiple occurrences of the same event within a subject will be counted once in the maximum intensity category (severe > moderate > mild) and/or maximum drug relationship category (reasonable possibility, no reasonable possibility) and/or the earliest occurrence. If intensity or relationship is found to be missing the most severe occurrence will be imputed for that particular summary.

All AEs for each subject, including multiple occurrences of the same event, will be presented in full in a comprehensive listing including subject number, severity, seriousness, action taken, outcome, relationship to treatment, onset/stop date and duration.

Deaths that occur during the study will be listed in a data listing. The data listings for serious TEAE and TEAE leading to discontinuation will be generated as well.

[REDACTED]

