4.1 Number of subjects

It is planned to enroll up to 364 subjects who have completed Study MT-8554-A01. The study will be finished when approximately 100 subjects complete a 52-week open-label treatment period and 30-day follow-up.

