4.6 Study completion criteria

The study will be completed by the Sponsor when approximately 100 subjects complete a 52-week open-label treatment period and 30-day follow-up. Further treatment of study drug will not be allowed. At the completion of the study all subjects will be required to have EOT visit assessments within the defined visit window. All subjects will be followed for 30 days for AEs, and unresolved AEs or SAEs will be followed up according to Section 8.10.

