### **3.3 Sample Size and Power Considerations**

This study is an open-label extension of Study MT-8554-A01. There is no formal sample size estimation for this study. It is planned to enrol up to 364 subjects from Study MT-8554-A01. The subjects who have completed Study MT-8554-A01 and comply with all eligibility criteria may be enrolled into this study.

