## **6. GENERAL CONSIDERATIONS**

### **6.1 Descriptive Statistics**

Continuous data will be summarized descriptively using the number of observations, mean, standard deviation (SD), median, minimum and maximum. Categorical data will be summarized using frequency counts and percentages. The denominator for the percentages will be the total number of subjects in the treatment group and analysis population being presented, unless otherwise specified.

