### 8.2.7.2 Endometrial Histology (Endometrial Biopsy)

The Endometrial biopsy data will be summarized in the tables by treatment group of A01 and overall and visit as below.

1. Summary tables of proportion of subjects in abnormal\* category (Table 14.3.7.1)
2. Shift table for change in abnormal category from baseline to week 64 or EOT(Table 14.3.7.2)

\*Note: The histological categories are based on 2003 draft FDA guidance. [REDACTED]

[REDACTED]

[REDACTED]

[REDACTED]

The data from adjudication committee will be used for the analysis.

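### TEAEs are summarized only as crude percentages of all dosed women although follow-up is unequal by design; add person-time rates and a 52-week cumulative incidence

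*SAP*

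**What the plan says.** The primary objective in both documents is long-term safety and tolerability.

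**Follow-up.** Protocol 4.1 sets a ceiling, "It is planned to enroll up to 364 subjects who have completed Study MT-8554-A01", and a stopping rule: "The study will be finished when approximately 100 subjects complete a 52-week open-label treatment period and 30-day follow-up". Under Protocol 4.6 no drug is given after that point, and "At the completion of the study all subjects will be required to have EOT visit assessments within the defined visit window". Women may also withdraw at any time (Protocol 4.5.2), and continuing after the dose change required a new consent (Protocol 5.1). SAP 8.4 notes that some women had already finished or left by then. SAP 3.3 adds: "There is no formal sample size estimation for this study".

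**Measure.** SAP 8.2.1 states: "The frequency and incidence of TEAEs will be summarized by System Organ Class (SOC) and Preferred Term (PT) by treatment" group of the parent study and overall. A woman counts once per event. SAP 6.1 sets the default denominator: "The denominator for the percentages will be the total number of subjects in the treatment group and analysis population being presented", unless otherwise specified. The safety population is everyone with at least one dose (SAP Table 2), and SAP 8.2.1 specifies no other denominator.

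**Time.** Table 14.3.1.3 presents TEAEs by time of onset, using the earliest occurrence, with no at-risk denominator stated. Exposure has its own table, 14.1.5. Time from first A02 dose to the event is derived in SAP 7.3.2.3. None of these is linked to the incidence percentages.

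**Biopsy.** SAP 8.2.7.2 plans a "Shift table for change in abnormal category from baseline to week 64 or EOT" (Table 14.3.7.2). EOT assessments are also made at early withdrawal.

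**The concern.** A long-term safety study should tell the reader how likely an event is over a year of treatment and whether new events appear late. A count divided by everyone dosed answers the first question only if nearly everyone is followed for a year. Here the stopping rule and early withdrawal both shorten follow-up, and a woman who leaves at week 10 stays in the denominator as if she had been watched for 52 weeks.

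The onset table has a related weakness. If the SAP 6.1 default applies, women who have left still count in the late intervals, so the percentages fall with time even when the hazard does not. A reader could take that fall as evidence that events subside.

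Both effects make the drug look safer on the primary objective.

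**Working it through.** **Inputs from the documents.** Enrolment ceiling N = 364 and about C = 100 one-year completers (Protocol 4.1). There is no sample-size calculation to reproduce. If both figures were met exactly, 100/364 = 27.5% complete and 264/364 = 72.5% have less than a year.

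**Assumed, because not given.** Drop-out pattern, accrual period, actual enrolment and A02 event rates. Exit is taken as unrelated to event risk.

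**Step 1: expected crude percentage.** With onset distribution F and follow-up c among the 264 non-completers,

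crude = [100·F(52) + 264·mean F(c)] / 364.

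Under a constant hazard with one-year risk p, h = −ln(1−p). For exits spread evenly over the year, mean F(c) = 1 − (1−e^−h)/h.

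- p = 10%: h = 0.10536, mean F(c) = 0.0509, crude = (10 + 13.43)/364 = **6.4%**.
- p = 5%: h = 0.05129, mean F(c) = 0.0252, crude = (5 + 6.66)/364 = **3.2%**.
- p = 10%, earlier exits (density 2(1−t)): (10 + 264 × 0.0342)/364 = **5.2%**.
- p = 10%, later exits (density 2t): (10 + 264 × 0.0675)/364 = **7.6%**.
- p = 10%, only 200 enrolled, even exits: (10 + 100 × 0.0509)/200 = **7.5%**.

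In a 2,000-run simulation of the even-exit case at p = 10%, the crude percentage averaged 6.5% and one minus Kaplan-Meier at week 52 averaged 10.0%.

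**Step 2: dependence on exit pattern and onset.** Ratio of crude to true one-year risk, with 364 dosed and 100 completers:

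| The other 264 women | Constant hazard | Onset weeks 26–52 only | Onset first 4 weeks only |
|---|---|---|---|
| all stop at week 8 | 0.39 | 0.27 | 1.00 |
| exit evenly, weeks 0–52 | 0.64 | 0.46 | 0.97 |
| exit evenly, weeks 26–52 | 0.82–0.83 | 0.64 | 1.00 |
| all stop at week 48 | 0.94–0.95 | 0.89 | 1.00 |

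The constant-hazard ratios barely change for risks from 1% to 20%.

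**Step 3: the stopping rule alone.** Suppose there is no drop-out and 364 enrol evenly over A weeks. The study ends at (100/364)·A + 52 + 30/7 weeks, and each woman has the lesser of 52 weeks and the time left after her entry.

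| A (weeks) | Share with full 52 weeks | Ratio, constant hazard (p = 10%) | Ratio, onset weeks 26–52 |
|---|---|---|---|
| 13 | 60% | 0.98 | 0.96 |
| 26 | 44% | 0.92 | 0.84 |
| 52 | 36% | 0.80 | 0.61 |
| 78 | 33% | 0.67 | 0.50 |

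**Step 4: the onset table under the default denominator.** Assume quarterly intervals and even exits. At the middle of the first quarter (100 + 264 × 0.875)/364 = 331/364 = 90.9% are still observed. At the middle of the last quarter it is (100 + 264 × 0.125)/364 = 133/364 = 36.5% (28.6% for earlier exits, 44.5% for later). With a constant hazard the last-quarter percentage would be about 133/331 = 0.40 of the first-quarter one. It would be about 2.7 times too low relative to the women still at risk (range 2.2 to 3.5).

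**The case against.** The strongest reply is that the study is descriptive, that the protocol itself asks for frequency and incidence, and that neither document calls the percentage a 52-week risk. That stands to this extent: the crude table is customary and not an error. But a descriptive percentage is the main result for the primary objective, and readers will take it as the yearly risk unless one is given.

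Second, SAP 8.2.1 has redacted entries in its table list and a redacted closing block. An exposure-adjusted summary could be there. This limits the claim to the readable text.

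Third, the SAP already reports exposure, time of onset and a full listing. These help, but a reader cannot obtain person-time to first event or a week-52 risk from separate summary tables.

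Three stronger readings are tempting and are not supported:

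- A reader might infer that the design makes risks about 36% too low. That figure comes from an assumed even exit of 264 women. 364 is a ceiling, and the stopping rule alone gives anything from 2% to 33% too low over the accrual periods tried.
- A reader might infer that Table 14.3.1.3 certainly keeps departed women in each denominator. That is only the SAP 6.1 default, which can be overridden, and no table shell is available.
- A reader might infer that parent-study arms with more drop-out will look safer. No differential drop-out is documented.

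On biopsies, Table 14.3.7.1 is by visit, and SAP Table 3 limits Week 64 to Days 408–462. Pooling therefore affects only the shift table.

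Finally, a pooled 52-week estimate has its own weaknesses. It mixes 10 mg and 5 mg, and Kaplan-Meier assumes that leaving is unrelated to event risk. Both points stand and shape the fix.

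**Conclusion.** The point holds as a cheap improvement, not as a fault in the crude tables. On the readable text, TEAE incidence is a percentage of all dosed women with unequal follow-up, so it is not a 52-week incidence and lies below one whenever women leave before events would have occurred.

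The direction is secure if exit is unrelated to event risk. The size is not: the ratio of crude to true risk runs from about 0.4 to 0.98 under a constant hazard, falls to 0.27 for onset only in weeks 26–52 with very early exit, and is 0.97 to 1.00 for events in the first four weeks. If few more than 100 women enrol, or most stay the year, little is lost. The 6.4% for a true 10% is an illustration, not an estimate for this trial.

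**What to change.** In SAP 8.2.1, before database lock, keep n (%) and add:

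1. **Rates.** Subjects with an event per 100 person-years, with person-time counted to the first event, for any TEAE, serious TEAEs, TEAEs leading to discontinuation and common preferred terms. Give them overall and split by time on 10 mg and time on 5 mg. State when time at risk ends: exposure in SAP 7.3.1.4 ends at the EOT visit, whereas Protocol 8 records AEs for a further 30 days.
2. **Cumulative incidence at 52 weeks** from the first A02 dose for the same categories, labelled as covering the mixed 10 mg then 5 mg regimen. Treat discontinuation that may be related to AE risk as a competing event, or state the independent-censoring assumption.
3. **Table 14.3.1.3.** Use as denominator the women still under observation at the start of each interval.

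Secondary: show shift Table 14.3.7.2 separately for Week 64 biopsies and for earlier EOT biopsies.

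If a redacted table already provides any of this, cross-refer to it instead.

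**Cost.** SAP wording and modest programming, with no new data, since exposure and time to event are already derived. Reported risks will be higher than the crude percentages, and the 52-week estimate will rest on a stated assumption about censoring.

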10.3 Statistical analysis

10.3.1 General considerations

A SAP containing definitions of analysis populations and baseline points, detailed data handling, analysis methods, detailed methods and criteria for the interim analysis, and outputs (tables, figures and listings) will be developed and approved prior to database lock. Additional analysis may be performed if deemed necessary. Any deviations from the planned analysis will be described and justified in a separate document and in the CSR.

The statistical analysis will be performed using SAS® Version 9.2 or higher. The Safety population will be used for all analyses and summaries. Point estimates will have 2-sided 95% CIs where applicable.

Where appropriate, data will be summarized descriptively (frequency and percent will be summarized for categorical variables; mean, standard deviation, median, minimum, and maximum will be presented for continuous variables) by study visit and by treatment group.

All individual subject data will be listed, where applicable. The baseline value of Study MT-8554-A02 is the last valid values prior the first dose of Study MT-8554-A02. The baseline value of Study MT-8554-A01 and Study MT-8554-A02 will be used as appropriate.

The Study MT-8554-A01 data are combined with Study MT-8554-A02 data for summary tables and graphs as needed.

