**Table 2 Analysis populations**

Analysis Population	Definition
Safety(SAF) population	All subjects who receives at least 1 dose of study medication
Intent-to-treat (ITT) population	All subjects who have at least 1 post-baseline exploratory assessment

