### 7.3.2.3 Duration of the AE and Time to the AE

Duration of the AE and time to the AE occurrence from start of study A02 medication will be calculated and presented in days, where AE duration = AE stop date – AE start date + 1 and the time to the AE occurrence = AE start date – first study A02 dose date + 1.

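### The TEAE time-of-onset table (14.3.1.3) divides first onsets by everyone dosed, so its percentages cannot be read as a time trend: per unit time they fall even at constant risk

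*SAP*

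**What the plan says.** SAP 8.2.1 lists a table of TEAEs by SOC, PT and time of onset (Table 14.3.1.3). The rule below the list works at subject level: "multiple occurrences of the same event within a subject will be counted once in the summaries by SOC and PT". For tables with a further classification, the single count goes to the maximum intensity "and/or maximum drug relationship category (reasonable possibility, no reasonable possibility) and/or the earliest occurrence". The last clause naturally governs the onset table, as maximum intensity governs Table 14.3.1.4 and maximum relationship Table 14.3.1.7.

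SAP 6.1 sets the denominator: "The denominator for the percentages will be the total number of subjects in the treatment group and analysis population being presented, unless otherwise specified". The readable text of 8.2.1 gives no other. Protocol 10.3.1 says "The Safety population will be used for all analyses and summaries", and SAP Table 2 defines that population as "All subjects who receives at least 1 dose of study medication".

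SAP 7.3.2.3 derives time to onset ("the time to the AE occurrence = AE start date – first study A02 dose date + 1"), but the readable text plans no at-risk denominator, person-time rate or Kaplan-Meier estimate from it. Neither document states the onset intervals. Recurrences are kept in a listing only.

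**The concern.** The numerator is women with a first onset of the term in the interval. The denominator is all women ever dosed. It still includes women who have already had the term, and can no longer be counted, and women who are no longer observed. Both groups grow with time, so later intervals are diluted.

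The primary objective is long-term safety and tolerability, and there is no control arm in which the same artefact would show. Table 14.3.1.3 is the only readable AE table by time since the start of A02 treatment. A decline produced by the counting could be taken for events that settle with continued use. It could also be taken for an effect of the change from 10 mg to 5 mg, because SAP 8.4 does not list this table among those compared before and after the change. The error runs in the reassuring direction.

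**Working it through.** The documents give no figure on this point, so there is none to reproduce. The yearly risks below are assumptions, shown over a range.

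**Inputs.** 52 weeks of treatment (SAP 3.1); up to 364 enrolled and a study that ends at about 100 completers (Protocol 4.1); visit spacing of 8, 8, 12, 12 and 12 weeks (SAP 3.1), used as one possible set of onset intervals.

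**Step 1: full follow-up, constant risk, four 13-week quarters.** For yearly risk p, the weekly hazard is h = −ln(1 − p)/52. The planned percentage for the interval from a to b is exp(−ha) − exp(−hb). At p = 30%, the proportions still free of the term at 0, 13, 26, 39 and 52 weeks are 1, 0.9147, 0.8367, 0.7653 and 0.7000. Successive differences are 8.53, 7.80, 7.14 and 6.53%.

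| Yearly risk | Q1 | Q2 | Q3 | Q4 | Q4/Q1 |
|---|---|---|---|---|---|
| 5% | 1.27 | 1.26 | 1.24 | 1.23 | 0.96 |
| 10% | 2.60 | 2.53 | 2.47 | 2.40 | 0.92 |
| 30% | 8.53 | 7.80 | 7.14 | 6.53 | 0.77 |
| 50% | 15.9 | 13.4 | 11.3 | 9.5 | 0.59 |

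Conversely, a row that looks flat can hide a rising risk. If 12.5% of all women have a first onset in each quarter (50% in total), the Q4 to Q1 hazard ratio is ln(0.625/0.500) / ln(1/0.875) = 0.2231/0.1335 = 1.67.

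**Step 2: add incomplete follow-up.** Assume exponential loss from 364 to 100 over 52 weeks: d = ln(364/100)/52 = 0.0248 per week. The planned percentage becomes [h/(h+d)] × [exp(−(h+d)a) − exp(−(h+d)b)].

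| Yearly risk | Q1 | Q2 | Q3 | Q4 |
|---|---|---|---|---|
| 5% | 1.09 | 0.78 | 0.56 | 0.40 |
| 10% | 2.22 | 1.57 | 1.11 | 0.78 |
| 50% | 13.66 | 8.32 | 5.06 | 3.08 |

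Q4/Q1 is now exp(−39h) × exp(−39d). The second factor, from loss alone, is 0.379. At 5% yearly risk the first factor is 0.96, so nearly all of the fall comes from keeping unobserved women in the denominator. Steps 1 and 2 are the two ends of the range: no loss, and the largest loss that the planned numbers allow.

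**Step 3: unequal intervals.** With the visit spacing and full follow-up, the planned table reads 1.61, 1.58, 2.33, 2.27, 2.22% at 10% yearly risk; 5.3, 5.1, 7.1, 6.5, 6.0% at 30%; and 10.1, 9.1, 11.9, 10.2, 8.7% at 50%. Interval length and depletion now pull in opposite directions, and neither can be separated from a change in risk.

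**Step 4: the alternative count.** Take women with any onset in the interval over women observed at its start, with recurrences at the same rate as first onsets. With full follow-up this gives 1 − exp(−13h) in every quarter: 1.27% (5% yearly risk), 2.60% (10%), 8.53% (30%) and 15.91% (50%). Under the loss in step 2 a 5% term reads 1.09% in every quarter: flat, and slightly low because some women leave within the quarter. With 8- and 12-week intervals a 30% term reads 5.3% and 7.9% by length alone, so equal intervals or person-time rates are needed.

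**The case against.** The defence is substantial. This is one descriptive table with no test attached. When a term first occurred is a legitimate question, and counting each woman once makes the table reconcile with Table 14.3.1.2. Overall incidence is unaffected, and every recurrence is listed with its onset date. Most PT rows will be too rare for the earliest-occurrence rule to matter. All of this stands. It limits the size of the point but does not repair the denominator.

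Four stronger readings are tempting, and the documents do not support them.

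- A reader might infer that the printed percentages must fall over the year. That is guaranteed only for equal intervals or per unit time. The SAP does not define the intervals, and step 3 shows percentages that rise from first to last at 10% and 30% yearly risk.
- A reader might infer that a woman disappears from the table after her first event of any kind. The rule applies to the same event, so a later, different PT is counted in its own row.
- A reader might apply the high overall AE incidences reported for A01 in SAP 8.5 to an any-TEAE row and obtain a dramatic decline. The documents do not show that Table 14.3.1.3 has such a row, or that those incidences would persist through A02.
- A reader might infer that nothing else shows AEs over time. SAP 8.4 and 8.5 plan TEAE summaries before and after the dose change, though these compare two dose periods and not time since starting A02.

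Two bullets and a closing block of 8.2.1 are blacked out, and the table shells are not in the documents. A different denominator could be stated there, as the exception clause in SAP 6.1 would allow.

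**Conclusion.** The point holds in this limited form. As the readable SAP stands, Table 14.3.1.3 puts first onsets over everyone dosed, and at constant risk that quantity falls per unit time. With full follow-up and equal quarters the effect can be ignored at or below 10% yearly risk, at most 0.2 percentage points. It is material for common terms or SOC rows, where the last quarter shows 0.77 of the first at 30% yearly risk and 0.59 at 50%. The larger distortion comes from incomplete follow-up, which affects rare and common terms alike: a factor of 0.379 between the first and last quarters if 364 women decline exponentially to 100.

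These sizes assume constant hazards, the stated yearly risks and, for the last figure, full enrolment and exponential loss. The direction per unit time needs only constant risk and the all-dosed denominator. The table should be changed because it is the readable AE table closest to the long-term question and its error reassures. Confidence is moderate, given the redactions.

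**What to change.** In SAP 8.2.1, for Table 14.3.1.3 only:

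1. State the onset intervals, preferably of equal length.
2. In each interval, count women with at least one onset of the term, first or recurrent. Divide by the women still under AE observation at the start of the interval, and print that number. Draw numerator and denominator from the same women. Protocol 4.5.1 aims to keep women on study after they stop treatment, and Protocol 8 records AEs until 30 days after the last treatment visit. A denominator of women on treatment would therefore not match a numerator that includes onsets after stopping.
3. If the intervals are unequal, or many women leave within them, give events per person-time instead.
4. If a first-onset version is kept, remove women who have already had the term from the later denominators.

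Leave the once-per-subject rule for the other AE tables. The cost is SAP wording and the reprogramming of one table from onset dates already collected. The drawback is that a woman can appear in several intervals, so the columns no longer add up to Table 14.3.1.2; a footnote should say so.
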